4.1 Study Objectives

Our **study objectives** are as follows:

1. Effectiveness. Compare the effectiveness of Engagement-Focused Care Coordination and PSE on key patient-reported outcomes, including depression and anxiety symptoms, coping skills, self-efficacy, parenting stress, and child behavior; and on mothers' engagement with formal

mental health treatment.

2. Heterogeneity of Treatment Effect. Determine whether timing of intervention delivery (pregnancy or postpartum) moderates the difference between the two comparators.
3. Implementation. Conduct qualitative interviews with patients, clinic administrators, staff, and intervention providers to understand perspectives and organizational cultures that serve as barriers or facilitators to implementing the comparators in real world practice settings.

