4.2 Study Outcome Measures

4.2.1 Primary Outcome Measures

Each subject will have 12-months of follow-up. All outcomes will be assessed at 2-month intervals.

Our primary outcome measure is depressive symptomatology, as measured by the QIDS – and operationalized as an incident rate of moderate to severe episodes over time and as symptom trajectories.

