4.2.2 Secondary Outcome Measures

We have identified a series of additional patient-centered outcomes pertaining to symptom relief, behavioral activation, parenting stress, self-efficacy, coping skills, and child behavior.

- a. Symptom relief and behavioral activation. Structured surveys and interviews have consistently demonstrated that the most meaningful outcomes to patients involve a combination of symptom relief and functional improvement [13]: symptom relief is more relevant when linked to the feeling of being activated (Spanish word used, ‘áñimo’), ‘being in a better place,’ or feeling like one is actively ‘climbing out of the hole.’ In addition to the QIDS, we will also administer the Beck Anxiety Inventory every other month will allow us to follow anxiety symptom trajectories. We will accompany these measures with the Behavioral Activation for Depression Scale.
- b. Self-efficacy and coping skills. Engagement Interview and PSE participants tend to discuss self-efficacy and coping skills in terms of their ability to manage a stressful event or get through an episode of demoralization. The Brief COPE measures ways of coping with stress through various scales, including (but not limited to): self-distraction, active coping, denial, substance use, and use of emotional support.
- c. Quality of Life. We will be using the Individual Burden of Illness Index for Depression, which incorporates multi-dimensional patient-reported outcomes from the QIDS, Quality of Life Enjoyment and Satisfaction Questionnaire - Short Form (Q-LES-Q-SF), and the Work and Social Adjustment Scale (WSAS).
- d. Parenting and Perceived Stress. Our parent advisors frequently raise the issue of stress – particularly as it relates to parenting. The Parenting Stress Index – Short Form is one of few valid and reliable tools that can assess a wide range of parenting behaviors in a single instrument, including attachment to child, social isolation, competence, relationship with spouse, and parental health. Cronbach’s α for the parent domain is 0.93 and the test-retest coefficient is 0.96 [17]. We will also

use the Perceived Stress Scale (PSS-14), the domains of which include unpredictability, lack of control, burden overload, and stressful circumstances.

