Following randomization, follow-up assessments will occur every 2 months for 12 months. Follow-up assessors will be blinded to each subject's allocation. The study team will use the preferred methods of contact indicated by the subject upon enrollment (ie. phone calls, texts, email, etc). We will assess certain outcomes measures – depressive symptomatology, anxiety symptom relief, and engagement, retention, and satisfaction with mental health services – at 2 months, 4 months, 8 months, and 10 months by phone. We will assess all outcome measures at 6 months and 12 months in person. Assessment windows will be 6 weeks long: 2 weeks before the “expected date” and 4 weeks after the “expected date.” Due to the written consent form having been updated on 4/28/2018, follow-up will also include the reconsenting of participants that were enrolled and consented with the 8/10/2017 consent form.

Outcome Measure	Measured by:
Depressive symptomatology	QIDS
Symptom relief and behavioral activation	Beck Anxiety Index; Behavioral Activation for Depression Scale
Self-efficacy and coping skills	Brief COPE
Parenting Stress	Parenting Stress Index – Short Form; Perceived Stress Scale
Child behaviors	Child Behavior Checklist (CBCL-1.5/5)
Engagement, retention, and satisfaction with mental health services	Collaborative Psychiatric Epidemiology Survey; Client Satisfaction Questionnaire (CSQ-8)

10 Assessment of Safety and Data Safety Monitoring Plan (DSMP)

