12.1 Study Hypotheses

Given PSE's penetrance and acceptability in prior studies [21-23], we hypothesize that its uptake will exceed 85% among women in this comparator; that it will provide sustained symptom relief; and that it will prevent the need for referring certain mothers (i.e. those with subsyndromal depression) to more formal care. By virtue of improved coping skills and behavioral activation, we hypothesize that PSE will make referrals to formal care more effective (for those who need it) than Engagement Interviewing alone. However, it is also important to assess the possibility that PSE may represent an unnecessary step that only serves to delay more definitive care and symptom relief. Our ultimate goal is to reduce disparities in access to mental health care for low-income mothers; and to improve outcomes for them and their children.

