b) Heterogeneity of Treatment Effect (HTE). The primary goal of our HTE analysis is to determine whether there is differential impact across our comparators, according to timing of screening (pregnancy vs. postpartum). Our hypothesis-driven HTE analysis thus answers the question: **When is the optimal time to deploy each comparator?** We will also explore HTE according to whether our participants have experienced violent trauma.

- Timing of Screening. The most likely HTE scenario is that Engagement-Focused Care Coordination will compare less favorably during pregnancy, when women are averse to medication treatment, and apt to misinterpret a referral to outside treatment as a road leading for pharmacotherapy.

- Trauma. In our own studies, we've documented a possible differential impact of PSE according to trauma history; however, because these data were not generated in the context of a comparative effectiveness trial, we consider our HTE-by-trauma analysis to be exploratory.

For both HTE analyses, we will use Rothman's methodology, evaluating moderation with stratified analyses (according to categorical predictors), followed by formal interaction term testing in our models. We will analyze repeated symptom measures as time-dependent covariates, and test them for interaction relative to concurrent outcomes. Within each subgroup, we will present treatment effect estimates and 95% confidence intervals.

3) **Adoption**. We will collect data related to the characteristics of the prenatal and pediatric clinics that may influence adoption (including size of staff, number of families served), and assess through qualitative techniques the potential for adoption of the intervention in these clinical venues.

4) **Implementation**. This is the subject of a separate IRB application.

5) **Maintenance**. Within the purview of this study, we will be unable to assess maintenance on the institutional level; however, at the individual level, our follow-up period will span 12 months.

13 Ethics/Protection of Human Subjects

This study is to be conducted according to applicable US federal regulations and institutional policies (which are based in federal regulations, guidance, and ICH Good Clinical Practice guidelines).

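### The HTE plan tests symptom scores measured after randomization as moderators, although these scales are trial endpoints that treatment is expected to change

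*Combined protocol and SAP*

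**What the plan says.** The HTE part of Section 12.3 (Statistical Methods) names two moderators: timing of screening, which is hypothesis-driven, and trauma history, which is exploratory. It gives the method as follows: "For both HTE analyses, we will use Rothman's methodology, evaluating moderation with stratified analyses (according to categorical predictors"), followed by tests of interaction terms. The next sentence reads: "We will analyze repeated symptom measures as time-dependent covariates, and test them for interaction relative to concurrent outcomes". The paragraph closes by promising subgroup effect estimates with 95% confidence intervals.

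The target is Objective 2 in Section 4.1: "Determine whether timing of intervention delivery (pregnancy or postpartum) moderates the difference between the two comparators".

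On the symptom scales themselves:
- Section 4.2.1: "Our primary outcome measure is depressive symptomatology, as measured by the QIDS".
- Section 4.2.2: "we will also administer the Beck Anxiety Inventory every other month will allow us to follow anxiety symptom trajectories".
- Section 9, Follow-Up Procedures: "follow-up assessments will occur every 2 months for 12 months". For months 2, 4, 8 and 10 it says: "We will assess certain outcomes measures – depressive symptomatology, anxiety symptom relief, and engagement, retention, and satisfaction with mental health services". All measures are taken at months 6 and 12.
- Section 12.1, on what PSE is expected to do: "that it will provide sustained symptom relief".

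**The concern.** A moderator has to be a characteristic that treatment cannot have altered. A symptom score taken at a follow-up visit is partly a result of the assigned arm. Women with low scores at month 4 in one arm are not exchangeable with women with low scores at month 4 in the other, so contrasts between arms within levels of that score lose the protection of randomization. An arm-by-current-symptom interaction would be read as showing who benefits, when it partly shows who has already responded.

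Service engagement raises a further problem. Section 3.1 describes PSE as followed by referral to further treatment when symptoms persist. A link between current symptoms and service use that differs by arm is thus partly built into the intervention and need not show differential benefit.

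Objective 2 is also at stake. It has its own power statement and is meant to inform when each comparator should be deployed. An analyst who put concurrent symptoms into the arm-by-timing model would condition on part of the effect being estimated and could hide real moderation.

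**Working it through.** **1. Which measures are meant.** The words for time-dependence and concurrency in the sentence point to values taken during follow-up. The symptom scales that the text schedules repeatedly are the QIDS and the Beck scale. Post-traumatic symptoms appear only in the baseline survey described in the synopsis. Section 4.2.1 also says that all outcomes are assessed every two months, while Section 9 limits the full set to months 6 and 12. On either schedule the repeated scales are trial outcomes. (The schedule-of-events figure is not shown in the copy reviewed, so this rests on the text.) Nothing restricts the covariates to baseline or lagged values, and no mediation or other causal framework is given.

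**2. The plan's own HTE power.** Inputs from Section 12.2: 100 per arm, equal recruitment before and after birth (50 per cell), rates 0.45 vs 1.2 prenatally and 1.15 vs 1.2 postpartum, two-sided alpha 0.05.
- Log ratio of rate ratios: ln[(0.45/1.2)/(1.15/1.2)] = ln(0.375/0.9583) = ln(0.391) = -0.938.
- SE = sqrt[1/(50×0.45) + 1/(50×1.2) + 1/(50×1.15) + 1/(50×1.2)] = 0.3085.
- z = 0.938/0.3085 = 3.04; power = Φ(3.04 - 1.96) = 0.860.

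This reproduces the stated 86%. The formula has four cell rates and no covariate, so the figure describes an interaction not adjusted for concurrent symptoms.

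**3. Effect of losing part of the interaction.** With the SE held at 0.3085:

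| Log interaction left | Ratio of rate ratios | Power |
|---|---|---|
| 100% | 0.391 | 86% |
| 70% | 0.52 | 57% |
| 50% | 0.63 | 33% |
| 40% | 0.69 | 23% |
| 0% | 1.00 | 5% |

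**4. How much could be lost.** Simulation with the plan's HTE rates, 50 women per cell, six assessments and the plan's within-subject correlation of 0.6; 500 runs per setting. Each visit has an episode when a latent normal score exceeds a threshold set by rate/6 (for example 1.2/6 = 0.20). A concurrent scale has correlation ρ with that score and shows a share k of its standardized treatment effect. Neither ρ nor k is given in the documents. The model is log-link Poisson with arm, timing and arm-by-timing, and standard errors clustered by woman. It was fitted without the scale, with it, and with it plus its interaction with arm.

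| ρ | k | Left, scale added | Left, scale and arm-by-scale added |
|---|---|---|---|
| 0.5 | 0 | 98% | 98% |
| 0.7 | 0 | 102% | 102% |
| 0.5 | 0.5 | 76% | 75% |
| 0.7 | 0.5 | 69% | 67% |
| 0.5 | 1 | 58% | 54% |
| 0.7 | 1 | 37% | 34% |
| 0.9 | 1 | 19% | 16% |

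The range is 100 - 76 = 24% to 100 - 16 = 84% lost when k is 0.5 to 1. The pair ρ = 0.9, k = 0.5 was not run. In a linear model the share left is about 1 - ρk, which for that pair gives 1 - 0.45 = 0.55, inside the range.

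At ρ = 0.7, k = 1, simulated power falls from 54% unadjusted to 14% (12% with the arm-by-scale term). The 54% is below 86% because correlated visits make the episode counts more variable than Poisson. That is a separate matter; only the before-and-after comparison is relevant here.

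**The case against.** A reader might infer that the plan adjusts the Objective 2 estimate for concurrent symptoms and so removes the differential effect it seeks. The documents do not support that:

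- The words tying the method to both HTE analyses open the preceding sentence. The sentence on repeated symptoms stands alone, and nothing says that its terms enter the arm-by-timing model, the stratified estimates or the subgroup intervals. If it describes a separate analysis, the timing result is intact.
- It names neither the scale, nor the outcome, nor what the symptom score interacts with.
- HTE is powered on episode rates over the whole follow-up. A visit-level covariate does not obviously belong in a model for one count per woman.
- The main-effects analysis in Section 12.3 does not include the covariate.
- The size of any distortion follows largely from the chosen ρ and k. If treatment did not move the scale, adjustment would leave the estimate alone and could gain precision: in the k = 0 runs, power rose from 57% to 65% at ρ = 0.5 and from 50% to 69% at ρ = 0.7.

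All of this stands, and it limits the claim about Objective 2 to a conditional one. It does not rescue the symptom-moderator analysis itself, which lacks a randomized interpretation wherever it is fitted if arm is the other term. The k = 0 case also sits badly with the plan's own hypothesis of symptom relief. The lack of specification is a further reason to rewrite the sentence.

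**Conclusion.** The concern holds in two parts of different strength.

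First, an arm-by-current-symptom interaction does not estimate a randomized differential effect, because the scales are endpoints that treatment is expected to change. This needs no numerical assumption.

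Second, if these terms enter the arm-by-timing or arm-by-trauma model, they distort that interaction whenever treatment moves the scale. The loss was simulated for timing: about 24% to 84% of the log interaction for ρ of 0.5 to 0.9 and k of 0.5 to 1, and essentially none at k = 0. The documents fix neither ρ nor k, and they do not say whether the terms enter those models. Near-complete removal would need a covariate that almost duplicates the outcome and shares its whole effect; the plan does not state such a model.

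The primary comparison and the 86% HTE power figure are not affected as written.

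**What to change.** Replace the sentence in Section 12.3 with:

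> Effect modification will be tested only with characteristics measured before randomization (timing of screening, pregnancy vs. postpartum; trauma history; and, as exploratory, baseline symptom scores). Symptom scores measured after randomization will be used as outcomes but not as covariates or moderators in models that estimate the treatment effect or its moderation; any analysis of concurrent symptoms will be reported separately as exploratory and non-randomized, or as a mediation analysis with a stated estimand.

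This keeps the moderator as Section 12.3 defines it (timing of screening). Objective 2 in Section 4.1 refers to timing of intervention delivery, so the sponsor should confirm that the two are meant to be the same. The text leaves the QIDS and anxiety scales in place as outcomes and leaves room for a properly specified mediation analysis.

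The cost is one sentence. The synopsis already places depression and anxiety scales and trauma history in the baseline survey, so no new data, visits or participants are needed. What is given up is a concurrent-symptom interaction result that could not be read causally.
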